12. MEASUREMENT OF EFFECT

12.1 Antitumor Effect – Solid Tumors

For the purposes of this study, patients should be re-evaluated for response every 12 weeks. In addition to a baseline scan, confirmatory scans should also be obtained at least 4 weeks following initial documentation of objective response.

Response and progression will be evaluated in this study using the new international criteria proposed by the revised Response Evaluation Criteria in Solid Tumors (RECIST) guideline (version 1.1) [Eur J Ca 45:228-247, 2009]. Changes in the largest diameter (unidimensional measurement) of the tumor lesions and the shortest diameter in the case of malignant lymph nodes are used in the RECIST criteria.

12.1.1 Definitions

Evaluable for toxicity. All patients will be evaluable for toxicity from the time of their first treatment with Telaglenastat (CB-839) HCl.

Evaluable for objective response. All patients who receive at least one dose of study drug are evaluable for response. Patients who are enrolled but who do not receive any study drug may be replaced.

Evaluable Non-Target Disease Response. Patients who have lesions present at baseline that are evaluable but do not meet the definitions of measurable disease, have received at least one cycle of therapy, and have had their disease re-evaluated will be considered evaluable for non-target disease. The response assessment is based on the presence, absence, or unequivocal progression of the lesions.

12.1.2 Disease Parameters

Measurable disease. Measurable lesions are defined as those that can be accurately measured in at least one dimension (longest diameter to be recorded) as ≥ 20 mm (≥ 2 cm) by chest x-ray or as ≥ 10 mm (≥ 1 cm) with CT scan, MRI, or calipers by clinical exam. All tumor measurements must be recorded in millimeters (or decimal fractions of centimeters).

Note: Tumor lesions that are situated in a previously irradiated area are considered non-measurable unless there has been clear evidence of progression of the subject lesion following radiation therapy.

Malignant lymph nodes. To be considered pathologically enlarged and measurable, a lymph node must be ≥ 15 mm (≥ 1.5 cm) in short axis when assessed by CT scan (CT scan slice thickness recommended to be no greater than 5 mm [0.5 cm]). At baseline and in follow-up, only the short axis will be measured and followed.

Non-measurable disease. All other lesions (or sites of disease), including small lesions (longest diameter <10 mm [<1 cm] or pathological lymph nodes with ≥ 10 to <15 mm [≥ 1 to <1.5 cm] short axis), are considered non-measurable disease. Bone lesions, leptomeningeal disease, ascites, pleural/pericardial effusions, lymphangitis cutis/pulmonitis, inflammatory breast disease, and abdominal masses (not followed by CT or MRI), are considered as non-measurable.

Note: Cystic lesions that meet the criteria for radiographically defined simple cysts should not be considered as malignant lesions (neither measurable nor non-measurable) since they are, by definition, simple cysts.

‘Cystic lesions’ thought to represent cystic metastases can be considered as measurable lesions, if they meet the definition of measurability described above. However, if non-cystic lesions are present in the same patient, these are preferred for selection as target lesions.

Target lesions. All measurable lesions up to a maximum of 2 lesions per organ and 5 lesions in total, representative of all involved organs, should be identified as **target lesions** and recorded and measured at baseline. Target lesions should be selected on the basis of their size (lesions with the longest diameter), be representative of all involved organs, but in addition should be those that lend themselves to reproducible repeated measurements. It may be the case that, on occasion, the largest lesion does not lend itself to reproducible measurement in which circumstance the next largest lesion which can be measured reproducibly should be selected. A sum of the diameters (longest for non-nodal lesions, short axis for nodal lesions) for all target lesions will be calculated and reported as the baseline sum diameters. If lymph nodes are to be included in the sum, then only the short axis is added into the sum. The baseline sum diameters will be used as reference to further characterize any objective tumor regression in the measurable dimension of the disease.

Non-target lesions. All other lesions (or sites of disease) including any measurable lesions over and above the 5 target lesions should be identified as **non-target lesions** and should also be recorded at baseline. Measurements of these lesions are not required, but the presence, absence, or in rare cases unequivocal progression of each should be noted throughout follow-up.

12.1.3 Methods for Evaluation of Measurable Disease

All measurements should be taken and recorded in metric notation using a ruler or calipers. All baseline evaluations should be performed as closely as possible to the beginning of treatment and never more than 4 weeks before the beginning of the treatment.

The same method of assessment and the same technique should be used to characterize each identified and reported lesion at baseline and during follow-up. Imaging-based evaluation is preferred to evaluation by clinical examination unless the lesion(s) being

followed cannot be imaged but are assessable by clinical exam.

Clinical lesions Clinical lesions will only be considered measurable when they are superficial (e.g., skin nodules and palpable lymph nodes) and ≥ 10 mm (≥ 1 cm) diameter as assessed using calipers (e.g., skin nodules). In the case of skin lesions, documentation by color photography, including a ruler to estimate the size of the lesion, is recommended.

Chest x-ray Lesions on chest x-ray are acceptable as measurable lesions when they are clearly defined and surrounded by aerated lung. However, CT is preferable.

Conventional CT and MRI This guideline has defined measurability of lesions on CT scan based on the assumption that CT slice thickness is 5 mm (0.5 cm) or less. If CT scans have slice thickness greater than 5 mm (0.5 cm), the minimum size for a measurable lesion should be twice the slice thickness. MRI is also acceptable in certain situations (e.g. for body scans).

Use of MRI remains a complex issue. MRI has excellent contrast, spatial, and temporal resolution; however, there are many image acquisition variables involved in MRI, which greatly impact image quality, lesion conspicuity, and measurement. Furthermore, the availability of MRI is variable globally. As with CT, if an MRI is performed, the technical specifications of the scanning sequences used should be optimized for the evaluation of the type and site of disease. Furthermore, as with CT, the modality used at follow-up should be the same as was used at baseline and the lesions should be measured/assessed on the same pulse sequence. It is beyond the scope of the RECIST guidelines to prescribe specific MRI pulse sequence parameters for all scanners, body parts, and diseases. Ideally, the same type of scanner should be used and the image acquisition protocol should be followed as closely as possible to prior scans. Body scans should be performed with breath-hold scanning techniques, if possible.

PET-CT At present, the low dose or attenuation correction CT portion of a combined PET-CT is not always of optimal diagnostic CT quality for use with RECIST measurements. However, if the site can document that the CT performed as part of a PET-CT is of identical diagnostic quality to a diagnostic CT (with IV and oral contrast), then the CT portion of the PET-CT can be used for RECIST measurements and can be used interchangeably with conventional CT in accurately measuring cancer lesions over time. Note, however, that the PET portion of the CT introduces additional data which may bias an investigator if it is not routinely or serially performed.

Ultrasound Ultrasound is not useful in assessment of lesion size and should not be used as a method of measurement. Ultrasound examinations cannot be reproduced in their entirety for independent review at a later date and, because they are operator dependent, it cannot be guaranteed that the same technique and measurements will be taken from one assessment to the next. If new lesions are identified by ultrasound in the course of the study, confirmation by CT or MRI is advised. If there is concern about radiation exposure at CT, MRI may be used instead of CT in selected instances.

Endoscopy, Laparoscopy The utilization of these techniques for objective tumor evaluation is not advised. However, such techniques may be useful to confirm complete pathological response when biopsies are obtained or to determine relapse in trials where recurrence following complete response (CR) or surgical resection is an endpoint.

Tumor markers Tumor markers alone cannot be used to assess response. If markers are initially above the upper normal limit, they must normalize for a patient to be considered in complete clinical response. Specific guidelines for both CA-125 response (in recurrent ovarian cancer) and PSA response (in recurrent prostate cancer) have been published [JNCI 96:487-488, 2004; J Clin Oncol 17, 3461-3467, 1999; J Clin Oncol 26:1148-1159, 2008]. In addition, the Gynecologic Cancer Intergroup has developed CA-125 progression criteria which are to be integrated with objective tumor assessment for use in first-line trials in ovarian cancer [JNCI 92:1534-1535, 2000].

Cytology, Histology These techniques can be used to differentiate between partial responses (PR) and complete responses (CR) in rare cases (e.g., residual lesions in tumor types, such as germ cell tumors, where known residual benign tumors can remain).

The cytological confirmation of the neoplastic origin of any effusion that appears or worsens during treatment when the measurable tumor has met criteria for response or stable disease is mandatory to differentiate between response or stable disease (an effusion may be a side effect of the treatment) and progressive disease.

FDG-PET While FDG-PET response assessments need additional study, it is sometimes reasonable to incorporate the use of FDG-PET scanning to complement CT scanning in assessment of progression (particularly possible 'new' disease). New lesions on the basis of FDG-PET imaging can be identified according to the following algorithm:

- a. Negative FDG-PET at baseline, with a positive FDG-PET at follow-up is a sign of PD based on a new lesion.
- b. No FDG-PET at baseline and a positive FDG-PET at follow-up: If the positive FDG-PET at follow-up corresponds to a new site of disease confirmed by CT, this is PD. If the positive FDG-PET at follow-up is not confirmed as a new site of disease on CT, additional follow-up CT scans are needed to determine if there is truly progression occurring at that site (if so, the date of PD will be the date of the initial abnormal FDG-PET scan). If the positive FDG-PET at follow-up corresponds to a pre-existing site of disease on CT that is not progressing on the basis of the anatomic images, this is not PD.
- c. FDG-PET may be used to upgrade a response to a CR in a manner similar to a biopsy in cases where a residual radiographic abnormality is thought to represent fibrosis or scarring. The use of FDG-PET in this circumstance should be prospectively described in the protocol and supported by disease-specific medical literature for the indication. However, it must be acknowledged that both approaches may lead to false positive CR due to limitations of FDG-PET and biopsy resolution/sensitivity.

Note: A 'positive' FDG-PET scan lesion means one which is FDG avid with an uptake

greater than twice that of the surrounding tissue on the attenuation corrected image.

12.1.4 Response Criteria

12.1.4.1 Evaluation of Target Lesions

Complete Response (CR): Disappearance of all target lesions. Any pathological lymph nodes (whether target or non-target) must have reduction in short axis to <10 mm (<1 cm).

Partial Response (PR): At least a 30% decrease in the sum of the diameters of target lesions, taking as reference the baseline sum diameters.

Progressive Disease (PD): At least a 20% increase in the sum of the diameters of target lesions, taking as reference the smallest sum on study (this includes the baseline sum if that is the smallest on study). In addition to the relative increase of 20%, the sum must also demonstrate an absolute increase of at least 5 mm (0.5 cm). (Note: the appearance of one or more new lesions is also considered progressions).

Negative FDG-PET at baseline, with a positive FDG-PET at follow-up is a sign of PD based on a new lesion. No FDG-PET at baseline and a positive FDG-PET at follow-up: If the positive FDG-PET at follow-up corresponds to a new site of disease confirmed by CT, this is PD. If the positive FDG-PET at follow-up is not confirmed as a new site of disease on CT, additional follow-up CT scans are needed to determine if there is truly progression occurring at that site (if so, the date of PD will be the date of the initial abnormal FDG-PET scan). If the positive FDG-PET at follow-up corresponds to a pre-existing site of disease on CT that is not progressing on the basis of the anatomic images, this is not PD. (Note: A 'positive' FDG-PET scan lesion means one which is FDG avid with an uptake greater than twice that of the surrounding tissue on the attenuation corrected image.)

Stable Disease (SD): Neither sufficient shrinkage to qualify for PR nor sufficient increase to qualify for PD, taking as reference the smallest sum diameters while on study.

12.1.4.2 Evaluation of Non-Target Lesions

Complete Response (CR): Disappearance of all non-target lesions and normalization of tumor marker level. All lymph nodes must be non-pathological in size (<10 mm [<1 cm] short axis).

Note: If tumor markers are initially above the upper normal limit, they must normalize for a patient to be considered in complete clinical response.

Non-CR/Non-PD: Persistence of one or more non-target lesion(s) and/or maintenance of tumor marker level above the normal limits.

Progressive Disease (PD): Appearance of one or more new lesions and/or *unequivocal progression* of existing non-target lesions. *Unequivocal progression* should not normally trump target lesion status. It must be representative of overall disease status change, not a single lesion increase.

Although a clear progression of “non-target” lesions only is exceptional, the opinion of the treating physician should prevail in such circumstances, and the progression status should be confirmed at a later time by the review panel (or Principal Investigator).

12.1.4.3 Evaluation of Best Overall Response

The best overall response is the best response recorded from the start of the treatment until disease progression/recurrence (taking as reference for progressive disease the smallest measurements recorded since the treatment started). The patient's best response assignment will depend on the achievement of both measurement and confirmation criteria.

For Patients with Measurable Disease (*i.e.*, Target Disease)

Target Lesions	Non-Target Lesions	New Lesions	Overall Response	Best Overall Response when Confirmation is Required*
CR	CR	No	CR	≥4 wks. Confirmation**
CR	Non-CR/Non-PD	No	PR	≥4 wks. Confirmation**
CR	Not evaluated	No	PR	
PR	Non-CR/Non-PD/not evaluated	No	PR	Documented at least once ≥4 wks. from baseline**
SD	Non-CR/Non-PD/not evaluated	No	SD	
PD	Any	Yes or No	PD	no prior SD, PR or CR
Any	PD***	Yes or No	PD	
Any	Any	Yes	PD	

* See RECIST 1.1 manuscript for further details on what is evidence of a new lesion.

** Only for non-randomized trials with response as primary endpoint. It is required for this study.

*** In exceptional circumstances, unequivocal progression in non-target lesions may be accepted as disease progression.

Note: Patients with a global deterioration of health status requiring discontinuation of treatment without objective evidence of disease progression at that time should be reported as “*symptomatic deterioration*.” Every effort should be made to document the objective progression even after discontinuation of treatment.

For Patients with Non-Measurable Disease (*i.e.*, Non-Target Disease)

Non-Target Lesions	New Lesions	Overall Response
CR	No	CR
Non-CR/non-PD	No	Non-CR/non-PD*
Not all evaluated	No	not evaluated
Unequivocal PD	Yes or No	PD
Any	Yes	PD

* ‘Non-CR/non-PD’ is preferred over ‘stable disease’ for non-target disease since SD is increasingly used as an endpoint for assessment of efficacy in some trials so to assign this category when no lesions can be measured is not advised

FDG-PET response will not be used in the evaluation of best overall response.

12.1.5 Duration of Response

Duration of overall response: The duration of overall response is measured from the time measurement criteria are met for CR or PR (whichever is first recorded) until the first date that recurrent or progressive disease is objectively documented (taking as reference for progressive disease the smallest measurements recorded since the treatment started).

The duration of overall CR is measured from the time measurement criteria are first met for CR until the first date that progressive disease is objectively documented.

Duration of stable disease: Stable disease is measured from the start of the treatment until the criteria for progression are met, taking as reference the smallest measurements recorded since the treatment started, including the baseline measurements.

12.1.6 Progression-Free Survival

Progression-free survival (PFS) is defined as the time from the date of enrollment to the earliest date of progression or death. Progression-free survival (PFS) will be summarized by histology, if data warrant, using Kaplan-Meier quartile estimates along with 2-sided 95% CIs. If the subject does not have a documented date of progression or death, PFS will be censored at the date of the last adequate assessment. Further details on rules for censoring will be provided in the RAP. Progression-free survival (PFS) will be reported at the time of final analyses, regardless of the maturity of the data and then be updated when at least 70% of events are met.

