4.4 General Guidelines

Following registration, patients should begin protocol treatment within 28 days. Issues that would cause treatment delays should be discussed with the Principal Investigator. If a patient does not receive protocol therapy following registration, the patient's registration on the study may be canceled. The Study Coordinator should be notified of cancellations as soon as possible.

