9.3 Analysis of Secondary Endpoints

Secondary Endpoint:

1. Safety, progression free survival (PFS), time to progression (TTP) and overall survival (OS).

We will tabulate toxicity by cohort, type, severity and attribution. For patients with objectively measurable disease, as defined by RECIST v1.1, progression-free survival (PFS), time to progression (TTP), and overall survival (OS) will be calculated. We will estimate PFS and OS using the Kaplan-Meier method with time zero set to C1D1. OS is defined as time to death from any cause and PFS is defined as time to progression or death whichever comes first. OS is censored in patients not known to be dead at the time they were last known to be alive and PFS is censored in patients alive and progression-free at the date of last clinical follow-up. We will estimate the medians and select probabilities along with 95% confidence intervals. TTP will be estimated in a similar fashion and is defined as time to progression starting at C1D1. If more than a handful of patients die without progression, we will use Aalen-Johansen estimates to adjust for the competing risk of death.

2. Overall response rate and clinical benefit rate (CR, PR and SD > 12 weeks of Telaglenastat (CB-839) HCl)

Ho: CB 839 - Response Rate (RR) in disease	Ha: Target RR of combination in disease	Calculation	Statistic & Significance	Responsible investigator
5 %	25 %	ORR = pre-therapy sum longest diameters (5 or less lesions) / post-therapy sum longest diameters (same 5 or less lesions)	It is a one-sample binomial test with alpha = 5%.	[name]

3. Pharmacodynamic tumor oncometabolite levels of glutamine, glutamate, and aspartate between 0 and 8 hours post- Telaglenastat (CB-839) HCl dose among patients with persistent or recurrent metastatic cancers.

We will assess PD changes before and after treatment using the Wilcoxon signed rank test. For normally distributed data, with 27 patients we can detect a standardized mean difference (mean difference divided by standard deviation of differences) = 0.6 with 85% power assuming a two-sided 5% alpha. We will correlate these changes with response to treatment using Wilcoxon rank sum test. We will also perform a ROC curve analysis. With 27 patients, if the response rate is roughly 50%, we can detect an area under the ROC curve = 0.83 as significantly higher than 0.5 (the null value) with 85% power assuming a 5% alpha.

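### PFS is defined twice, with two start dates (C1D1 and enrollment) and two censoring rules, and nothing in the documents says which governs

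*Combined protocol and SAP*

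**What the plan says.** The two definitions agree on the event (progression or death, whichever is first) and differ on the rest.

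- **Section 9.3, origin:** "We will estimate PFS and OS using the Kaplan-Meier method with time zero set to C1D1". TTP uses the same clock: "TTP will be estimated in a similar fashion and is defined as time to progression starting at C1D1".
- **Section 9.3, censoring:** "PFS is censored in patients alive and progression-free at the date of last clinical follow-up". OS has separate wording: "OS is censored in patients not known to be dead at the time they were last known to be alive".
- **Section 12.1.6, origin:** "Progression-free survival (PFS) is defined as the time from the date of enrollment to the earliest date of progression or death".
- **Section 12.1.6, censoring:** where neither progression nor death is documented, "PFS will be censored at the date of the last adequate assessment". It adds: "Further details on rules for censoring will be provided in the RAP".

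Section 4.4 separates the two start dates: after registration, "patients should begin protocol treatment within 28 days". Section 6.4 and footnote 15 of the Study Calendar provide for contacts every three months after treatment. The footnote describes them as follow-up for survival and allows them to be made by telephone. The calendar schedules no scan after the end-of-treatment visit.

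**The concern.** Both sections are current body text. Neither refers to the other, and nothing in the documents ranks them. Two analysts, each following one section, would compute different PFS times for the same patients.

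The RAP does not resolve this on the face of the protocol. It is cited only for more detail on censoring, which leaves the origin open, and it is not among the documents.

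The patients whose censoring date is in doubt are foreseeable. Section 6.3 lists several reasons for stopping other than documented progression, among them adverse events, withdrawal and non-compliance. If the last clinical follow-up can be a telephone call, such patients accrue progression-free time during which nobody looked at the tumour.

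Section 13.1 gives the principal investigator and the statistician access to the data throughout. Unless the text is reconciled, the definition will be chosen by people who can already see the outcomes.

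**Working it through.** The plan states no sample size, power or event count for PFS, so there is no figure to reproduce. The contradiction is shown by comparing the texts; the arithmetic only gives its size.

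**1. Side by side**

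| | Section 9.3 | Section 12.1.6 |
|---|---|---|
| Time zero | C1D1 | enrollment |
| Event | progression or death | progression or death |
| Event-free patients censored at | last clinical follow-up (undefined) | last adequate assessment |
| Deferred elsewhere | nothing | further censoring detail, to the RAP |

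**2. Size of the origin difference**

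Input: a planned lag from registration to treatment of 0 to 28 days (Section 4.4), taking registration as enrollment. The wording is advisory, so 28 days is the planned limit and not a hard cap.

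PFS from enrollment = PFS from C1D1 + the patient's lag.

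- 14 days: 14/30.4375 = 0.46 months.
- 28 days: 28/30.4375 = 0.92 months.

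A lag common to all patients moves the median by exactly that lag. Lags that vary move it by some intermediate amount.

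**3. Size of the censoring difference**

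The term in Section 9.3 can be read in two ways.

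- *Any follow-up contact.* Section 6.4 uses the word follow-up for the three-monthly contacts after treatment.
- *A visit with tumour assessment.* Footnote 15 labels those contacts as being for survival, and OS has its own last-known-alive rule. Under this reading the two censoring rules nearly coincide.

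The first reading was illustrated by simulating 200,000 patients from C1D1.

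- From the documents: scans every 56 days with a ±7-day window plus an end-of-treatment scan (Study Calendar, footnote 7); contacts every 3 months after treatment. Section 12.1 says re-evaluation every 12 weeks; the calendar's 8 weeks was used.
- Assumed: exponential progression, median 2.8 months; exponential time from progression to death, median 6 months; independent discontinuation at 0.081, 0.035 or 0 per month; data cut uniform over 6 to 30 months.
- Progression and death count as events under both rules. Kaplan-Meier is read at 6 months.

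| Stop without documented progression | Censor at last contact | Censor at last scan | Gap (points) |
|---|---|---|---|
| 24% | 33.4% | 29.4% | 4.0 |
| 12% | 29.2% | 27.2% | 2.0 |
| 0% | 25.4% | 25.2% | 0.2 |

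A repeat run gave 33.5% v 29.6%, 29.1% v 27.1% and 25.5% v 25.2%.

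For scale, the standard error of a 30% rate in 27 patients is √(0.3 × 0.7/27) = 0.088, and 4.0/8.8 = 0.45.

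**4. Sensitivity to the assumed model**

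A simpler model used exponential PFS with median 2, 4 or 6 months, 10% to 30% of patients censored, and last contact 3 months after the last scan. Its gaps at 6 months ran from 0.9 points (56.0% v 55.1%; median 6, 10% censored) to 6.4 points (25.7% v 19.3%; median 2, 30% censored). The largest is still below one standard error: √(0.193 × 0.807/27) = 0.076. The Kaplan-Meier median did not move in any of these runs.

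**The case against.** The strongest reply is that the conflict is small and its sensible resolution visible. Section 9 is the statistical section and uses C1D1 for PFS, OS and TTP. Section 12 itself counts best response and stable disease from the start of treatment. Enrollment is the outlier. This is a good argument for which origin to adopt, but the protocol does not state it, and 12.1.6 is the section headed with the endpoint's name.

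Other points reduce the size, and they stand:

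- **28 days is an edge value.** Eligibility, including measurable disease, is verified before registration, and the baseline scan must fall within 28 days before C1D1. A full 28-day lag therefore needs the scan and registration on about the same day, or a repeat scan. For women of childbearing potential, the eligibility pregnancy test is due within 14 days before treatment, so without a retest their lag is at most 14 days. A shift of 0.92 months in the median is a bound, not an expectation.
- **The censoring wording may not give different dates.** If it means a visit with tumour assessment, the gap is essentially nil. The RAP may also settle it.
- **The simulation documents no progression after end of treatment except through death.** Section 12.1.4.3 asks for every effort to document progression after stopping for symptomatic deterioration. In a re-run at 24% stopping, with progression documented one month after it occurs (assumed), the gap fell from 3.8 points to 2.5 if half of off-treatment patients were documented, and to 0.9 if all were. Even with no such documentation the medians differed by only about 0.06 months.
- **Last-scan censoring is not a cure.** In the table above its estimate still rises from 25.2% to 29.4% as stopping without progression goes from 0% to 24%.

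None of this removes the origin conflict, which does not depend on the RAP or on any simulation.

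**Conclusion.** The concern holds. The protocol gives two rules for one endpoint, which is a contradiction and not merely missing detail.

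The origin conflict is certain. It is worth up to 0.92 months per patient at the planned limit, and probably less in practice. The censoring conflict is certain in wording but conditional in effect. It changes results only if the last clinical follow-up includes contacts without imaging. In that case, 6-month PFS differs by about 1 to 6 points across the scenarios tried without progression documented after treatment, with little or no change in the median. Those figures rest on assumed progression times and stopping rates and are smaller than the sampling error of one 27-patient cohort.

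PFS is secondary and descriptive, with no test or decision attached. The primary response endpoint, the Simon rule and the sample size are untouched. The text should be corrected before PFS is analysed.

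**What to change.** Put one PFS definition in both sections:

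- **Time zero:** C1D1, matching OS and TTP. Delete the enrollment origin from 12.1.6.
- **Censoring:** patients without documented progression or death are censored at the last adequate tumour assessment, as 12.1.6 already says. Delete the clinical follow-up wording for PFS from 9.3.
- **OS:** keep the last-known-alive rule.

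If the RAP already settles both the origin and the censoring date, cite it as governing in both sections instead.

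The cost is wording in 9.3 and 12.1.6, with no new visits or data. Reported PFS may be slightly less favourable, because the clock starts later and unscanned time no longer counts. The number of patients who stop without documented progression should be reported beside the estimate, since the agreed rule does not remove their influence on it.
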